## **SECTION 1.**

Check the appropriate item:

■I am requesting a waiver of the requirement for the informed consent process.

■I am requesting an alteration of the informed consent process.

If you checked the box for this item, describe which elements of consent will be altered and/or omitted, and justify the alteration.

#### **SECTION 2.**

Explain how each condition applies to your research.

- a) The research involves no more than minimal risk to the subject.
- b) The rights and welfare of subjects will not be adversely affected.
- c) The research could not practicably be carried out without the requested waiver or alteration.
- d) Whenever possible, the subjects or legally authorized representatives will be provided with additional pertinent information after they have participated in the study.
- e) If the research involves using or accessing identifiable private information or identifiable biospecimens, the research could not practicably be carried out without using such information or biospecimens in an identifiable format.
  - Private information/specimens are "identifiable" if the investigator may ascertain the identity of the subject or if identifiers
    are associated with the information (e.g., medical records). This could be any of the 18 HIPAA identifiers including dates
    of service.
  - If not using identifiable private information or identifiable biospecimens, insert N/A below.

If you are requesting IRB approval to waive the requirement for signatures on informed consent forms, your research activities must fit into one of three regulatory options:

- 1. The only record linking the participant and the research would be the consent document, and the principal risk would be potential harm resulting from a breach of confidentiality (e.g., a study that involves participants who use illegal drugs).
- 2. The research presents no more than minimal risk to the participant and involves no procedures for which written consent is normally required outside of the research context (e.g., a cover letter on a survey, or a phone script).
- 3. The participant (or legally authorized representative) is a member of a distinct cultural group or community in which signing forms is not the norm, the research presents no more than minimal risk to the subject, and there is an appropriate alternative mechanism for documenting that informed consent was obtained.

Select the option below that best fits your study.

If the IRB approves a waiver of signatures, participants must still be provided oral or written information about the study. To ensure you include required elements in your consent document, use the **Cover Letter Template** as a guide. There is an English and a Spanish version.

## Option 1

#### Describe how your study meets these criteria:

- a) The only record linking the participant and the research would be the consent document:
- b) The principal risk would be potential harm resulting from a breach of confidentiality (i.e., a study that involves subjects who use illegal drugs).

Under this option, each participant (or legally authorized representative) must be asked whether (s)he wants to sign a consent document; if the participant agrees to sign a consent document, only an IRB approved version should be used.

## © Option 2

## Describe how your study meets these criteria:

- a) The research presents no more than minimal risk to the participant:
- b) Involves no procedures for which written consent is normally required outside of the research context (i.e. a cover letter on a survey, or a phone script):

### © Option 3

#### **RESEARCH DESCRIPTION**

0 unresolved comment(s)

You may attach a sponsor's protocol pages in the "Additional Information" section and refer to them where necessary in the Research Description. However, each prompt that applies to your study should contain at least a summary paragraph.

## Pro Tips:

- · Save your work often to avoid losing data.
- Use one of the attachment buttons in this section or under the Additional Information section to include supplemental
  information with your application. During the document upload process, you will be able to provide a brief description
  of the attachment.

#### **Background**

Include a brief review of existing literature in the area of your research. You should identify gaps in knowledge that should be addressed and explain how your research will address those gaps or contribute to existing knowledge in this area. For interventional research, search PubMed and ClinicalTrials.gov for duplicative ongoing and completed trials with same condition and intervention(s).

Biochemically recurrent (BCR) prostate cancer is an increasingly common disease state, with more than 25,000 cases annually [1]. Approximately 30-40% of all prostate cancer patients will develop biochemical or PSA recurrence within 10 years [2]. Whereas, highrisk localized prostate cancer patients (50-90%) have a higher rate of BCR progression [1]. In 2007, the American Urological Association defined biochemical recurrence after radical prostatectomy as an initial PSA level of = 0.2 ng/ml and with a second test confirming levels of > 0.2 ng/ml without radiological or clinical progression [3]. The natural history of PSA recurrence is usually long but can be varied. In a longitudinal cohort of 379 men followed for 22 years, the median time from PSA recurrence to prostate cancer death was not reached after 16 years [4]. In spite of this, prostate cancer deaths are occasionally seen as early as 1 year after PSA recurrence. Thus, although the natural history of recurrent prostate cancer is often one of a slowly progressive disease spanning years or decades, it can also be very rapid in a subset of patients. Moreover, 90% of all recurrences after radical prostatectomy were found within 5 years of prostatectomy as per Duke Prostate Cancer Database [5]. Patients who had early (=75 years) PSA recurrence have greater risk for cancer-death compared to those that recur >5 years post radical prostatectomy [5]. It has been shown that rapid prostate specific antigen doubling time (PSADT) is closely linked with risk for prostate cancer death and overall survival [4, 6]. Among men with a PSADT > 3 months after either RP or RT, PSADT as a continuous variable was significantly associated with prostate cancer death [6]. It has become common in clinical practice to make treatment decisions for men with PSA recurrence based on small changes in PSA level, PSADT, Gleason score and time to PSA recurrence [4, 8-10]. The clinical entity of recurrent prostate cancer is fairly common, affecting many current era patients and the subject of many encounters by urologists, radiation oncologists, and medical oncologists.

It is challenging to treat because of the absence of radiographic disease to monitor response. There is no clear consensus on when to begin androgen deprivation therapy (ADT), and the optimal duration of ADT in men with BCR. ASCO updated consensus panel recommendations in 2007, the authors refrained from strongly recommending early ADT initiation [11]. The Veterans Administration Cooperative Urological Research Group found no difference in overall survival when they compared early with deferred hormonal therapy [12]. Moul et al. reviewed data from 1,352 men with postsurgical PSA recurrence and found that, early ADT had no effect on time to metastasis [13]. However, among those with high-risk disease, (pathologic Gleason =8 or PSADT <12 months, early ADT (i.e., starting when the PSA was <5 or < 10 ng/ml) was associated with a 50% reduction in the risk of metastasis after a median follow-up of 3.7 years after PSA recurrence [13]. Unfortunately, follow-up was too short to assess the association between timing of ADT and prostate cancer mortality. Garcia-Albenix et al. analyzed 2,096 men experiencing biochemical recurrence after initial treatment from the CaPSURE registry (Cancer of the Prostate Strategic Urologic Research Endeavour) [14]. The effect of immediate ADT initiation (within 3 months of PSA relapse) on overall survival and prostate-cancer specific survival was evaluated, in comparison to deferred ADT (initiated at the development of metastases, symptoms or a short PSA doubling time). The adjusted mortality hazard ratio for immediate ADT versus deferred ADT was 0.91 (95% CI, 0.52-1.60), demonstrating no significant advantage to early initiation of ADT [14]. ADT confers significant decrements to functioning and quality of life, including sleep disturbance, hot flushes, breast enlargement and tenderness, mood swing, and increased risk of cardiovascular-related death have been observed [15-16]. Thus, the treatment decision for biochemical recurrence is complicated by the need to balance the efficacy of the therapy (gains in overall and diseasespecific survival) against minimization of side effects and decline in quality of life in this generally asymptomatic population.

Myriad alternative therapies for BCR have been investigated. Celecoxib treatment for post-RP BCR decreased PSA velocity [17]. Increased intake of vegetable proteins while decreasing animal protein and saturated fat consumption [18] or intake of a soy-based dietary supplement prolonged PSA velocity among men with BCR [19]. NCCN recommends in those population expectant management is also appropriate given the known toxicity of ADT and with the unclear benefit [20]. Thus, ongoing investigation and development of non-hormonal therapies is in demand.

## **Objectives**

List your research objectives. Please include a summary of intended research objectives in the box below.

Primary Objective

To determine the Maximum Tolerated Dose of Epidiolex (CBD) in patients with biochemically recurrent prostate cancer

Secondary Objectives

To fully assess the safety and tolerability of CBD in patients with biochemically recurrent prostate cancer.

To measure change in serial PSA and testosterone levels from baseline throughout the treatment period as an indication of biochemical response

To assess health-related quality of life (EORTC QLQ C-30 and PR-25)

**Exploratory Objective** 

Primary tumor from prostatectomy specimen will be assessed for CBD receptor 1 and 2 expression levels, among patients for whom archival surgical specimens are available.

## Study Design

Describe and explain the study design (e.g., observational, secondary analysis, single/double blind, parallel, crossover, deception, etc.).

- Clinical Research: Indicate whether subjects will be randomized and whether subjects will receive any placebo.
- Community-Based Participatory Research: If you are conducting community-based participatory research (CBPR), describe
  strategies for involvement of community members in the design and implementation of the study, and dissemination of results from
  the study.
- Qualitative research: Indicate ranges where flexibility is needed, if a fixed interview transcript is not available, describe interview
  topics including the most sensitive potential questions.
- Research Repositories: If the purpose of this submission is to establish a Research Repository (bank, registry) and the material
  you plan to collect is already available from a commercial supplier, clinical lab, or established IRB approved research repository,
  provide scientific justification for establishing an additional repository collecting duplicate material. Describe the repository design
  and operating procedures. For relevant information to include, see the UK Research Registry Guidance.

This is a phase I dose escalation study with expansion cohort. Dose escalation will be determined by a Bayesian optimal interval design (BOIN) design [41]. Patients are enrolled in cohorts with 3 patients in each cohort. The primary endpoint is the DLT rate at each dose level. DLT rate is calculated as the total number of patients experienced DLTs at the current dose level divided by the total number and number of patients treated at the current dose level using the DLT. The calculation of DLT rate will only include DLT evaluable patients. The primary endpoints is to find the maximum tolerated dose.

-In the first cohort, a patient is considered evaluable if he completes 75% of doses. Patients that are not evaluable will be replaced.

- In the dose expansion cohort, a patient is considered evaluable if he completes 75% of the planned dosing.

Dose Escalation / De-escalation Decision Rule

Number of patients Treated
Decision Rule 1 2 3 4 5 6 7 8 9
Escalate (or highest) if # DLT >= 0 0 0 0 1 1 1 1 2
De-escalate (or lowest) if # DLT >= 1 1 2 2 2 3 3 3 4
Eliminate (or stop) if # DLT >= -- -- 3 3 4 4 5 5 5

The secondary endpoints include assessment of biochemical response via serial PSA and serial testosterone levels, and health-related quality of life (as assessed by the EORTC QLQ C-30 and PR-25).

The correlative endpoint includes CBD receptor 1 and 2 expression levels.

Sample Size/Accrual Rate

We plan to enroll up to 9 DLT evaluable patients for dose escalation to establish the MTD.

Once we have established the MTD, we will begin treating 6 to 9 more patients at the MTD level in an expansion cohort to confirm safety and explore evidence of efficacy of the study treatment. The number of patients to be enrolled in expansion cohort depends on the number of non-DLT evaluable patients in the dose escalation part of the study. If all patients in the dose escalation part of the study are DLT evaluable, we will have enroll 9 more patients, otherwise, we will subtract the number of non-DLT evaluable patients from expansion cohort. The total sample size for this study is 18 (enrolled) patients with about 12 patients treated at the MTD.

Analysis of Primary Endpoint

The dose escalation and MTD will be determined by the posterior distribution of Pr(DLT) estimate [41]. The target toxicity probability is set at 30%. Safety and tolerability of Epidiolex will be monitored and assessed. AE counts will be summarized by descriptive statistics.

Analysis of Secondary Endpoints

Change of PSA and testosterone levels from baseline throughout the 90-day treatment period will be represented by longitudinal

profiles and analyzed by mixed effects model. Baseline is defined as the last non-missing PSA measurement prior to administrating study drug. PSA and testosterone levels may be categorized and summarized by response rates with confidence intervals.

The Quality of Life scores collected longitudinally will be analyzed using appropriate linear models for repeated measures data.

Analysis of Correlative Endpoints

Post-hoc analyses will be conducted on correlative endpoints with appropriate statistical methods depending on distribution and availability of collected data.

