# 9. STATISTICAL CONSIDERATIONS

# 9.1 Study Design/Endpoints

This is a phase I dose escalation study with expansion cohort. Dose escalation will be determined by a Bayesian optimal interval (BOIN) design [41]. The target DLT rate is 30%. Patients are enrolled in cohorts with 3 patients in each cohort. Enrollment will be temporarily halted after the last patient of each cohort is enrolled until all current patients are DLT evaluable or withdrawn from the study. A patient will be considered DLT evaluable if he completes at least 75% of the planned dose of Epidiolex in the first 30 days of the treatment, unless the reason is due to toxicity.

The primary objective is to evaluate the acute toxicity and long-term safety and tolerability of Epidiolex (CBD) in patients with biochemically recurrent prostate cancer. Acute toxicity of Epidiolex is evaluated through DLT rate, which is calculated as the total number of patients experienced DLTs at a dose level divided by the total number of patients treated at the corresponding dose level. The calculation of DLT rate will only include DLT evaluable patients. Patients who are not DLT-evaluable will not be replaced for the current cohort and will not be included in the calculation of DLT rate. At the end of the dose escalation part of the study, we will use the dose escalation/de-escalation decision rules (see section 9.1.1) to decide the dose level for dose expansion cohort. If the current dose at the end of dose escalation is already the highest available dose, and the decision rules did not indicate de-escalation or elimination, the highest dose level is deemed as safe for acute toxicity; otherwise, the dose recommended by the decision rule is the estimated MTD.

Following dose-escalation, an expansion cohort will be enrolled to confirm safety for acute toxicity, evaluate long-term safety and tolerability and explore evidence of efficacy of the study treatment. Long-term safety and tolerability are evaluated through the summary statistics of adverse events occurred within the 90-day follow-up period in patients who received any amount of study drug. The study treatment is deemed as not safe for long-term tolerability if any of the following criteria are met:

- More than 40% of the patients treated at the dose level selected for expansion cohort experienced grade 3 or higher AEs that are possibly/probably/definitely related to study treatment

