# 9.2 Sample Size/Accrual Rate

We plan to enroll up to 9 DLT evaluable patients for dose escalation. If 3 or more of the first 9 patients are not evaluable for DLT, additional cohort(s) will be enrolled to ensure at least 9 DLT evaluable patients for dose escalation. Once we have established the highest tolerated dose is deemed as acceptable for acute toxicity or estimated the MTD, we will begin treating 6 to 9 more patients in an expansion cohort to confirm safety for acute toxicity, evaluate long-term tolerability and explore evidence of efficacy of the study treatment. The number of patients to be enrolled in expansion cohort depends on the DLT rate during the dose escalation part of the study. The total planned sample size for this study is 18 (enrolled) patients with about 12 patients treated at the MTD or the highest planned dose.

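### Study Design and Section 9 differ on DLT evaluability, replacement and expansion size; taken literally, the Study Design rule leaves early-stopping DLT patients out of the primary DLT rate

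*Combined protocol and SAP*

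**What the plan says.** Two parts of the combined document describe the same design: the Study Design section of the IRB application's Research Description, and Section 9, Statistical Considerations.

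- **Evaluability.** Study Design: "In the first cohort, a patient is considered evaluable if he completes 75% of doses. Patients that are not evaluable will be replaced". For the expansion: "In the dose expansion cohort, a patient is considered evaluable if he completes 75% of the planned dosing". It also states: "The calculation of DLT rate will only include DLT evaluable patients". Section 9.1 repeats that restriction but defines DLT-evaluable as completing "at least 75% of the planned dose of Epidiolex in the first 30 days of the treatment, unless the reason is due to toxicity".
- **Replacement.** Study Design replaces non-evaluable patients. Section 9.1: "Patients who are not DLT-evaluable will not be replaced for the current cohort and will not be included in the calculation of DLT rate". Section 9.2 adds a later remedy: "If 3 or more of the first 9 patients are not evaluable for DLT, additional cohort(s) will be enrolled to ensure" at least 9 evaluable patients.
- **Expansion size.** Both texts give 6 to 9. Study Design enrols 9 if every escalation patient is evaluable; "otherwise, we will subtract the number of non-DLT evaluable patients from expansion cohort". Section 9.2: "The number of patients to be enrolled in expansion cohort depends on the DLT rate during the dose escalation part of the study".
- **Common ground.** Both give a 30% target DLT rate, cohorts of 3, up to 9 evaluable patients in escalation and a total of 18 enrolled.

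Section 9.4 also restricts the secondary-endpoint analyses to patients who are DLT-evaluable.

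**The concern.** The DLT rate is the primary endpoint in Study Design and the acute-toxicity measure in Section 9.1, and DLT counts drive every dose decision. Both texts compute the rate in evaluable patients only, so the definition of evaluable decides which DLTs are seen. A DLT is a likely reason for stopping drug early. A completion threshold with no toxicity exception can therefore remove the very patients the endpoint is meant to count, and the error runs in one direction, towards a lower apparent rate.

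The replacement and expansion rules conflict more directly. One text replaces where the other does not, and each names a different quantity as fixing the size of the expansion. Staff working from different parts of the document could enrol different numbers of men and reach different dose decisions from the same events.

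**Working it through.** **The plan's own figures.** The total of 18 reproduces as 9 + 9. The Section 9.1.1 table also reproduces. Take φ = 0.30 with φ₁ = 0.6φ = 0.18 and φ₂ = 1.4φ = 0.42 (assumed; the documents do not state them):

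- λₑ = ln(0.82/0.70) / ln[(0.30 × 0.82)/(0.18 × 0.70)] = 0.2365
- λ_d = ln(0.70/0.58) / ln[(0.42 × 0.70)/(0.30 × 0.58)] = 0.3585

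The escalation bound is floor(nλₑ) and the de-escalation bound is ceil(nλ_d). Elimination requires P(rate > 0.30 | data) > 0.95 under a Beta(1,1) prior with n ≥ 3 (also assumed). All 27 cells for n = 1 to 9 match. No stated number is wrong; the problem lies in what feeds the table.

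**Evaluability: one cohort, two readings.** Suppose 2 of 3 men have a DLT and stop before 75% of doses because of it. Decisions are from the Section 9.1.1 table.

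| Rule | DLTs / evaluable | Decision |
|---|---|---|
| Section 9.1 | 2/3 | De-escalate (bound at n = 3 is 2) |
| Study Design, before replacement | 0/1 | Escalate (bound at n = 1 is 0) |
| Study Design, both replacements DLT-free | 0/3 | Escalate (bound at n = 3 is 0) |

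**Evaluability: illustrative size of the bias.** Let p be the true DLT rate and s the share of DLT patients excluded for stopping early. The documents do not give s. With all DLT-free patients evaluable,

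apparent rate r = p(1 − s) / [p(1 − s) + (1 − p)].

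At p = 0.30, for a cohort of 3 evaluable patients:

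| s (assumed) | r | P(0 of 3, escalate) = (1 − r)³ | P(2 or more of 3) |
|---|---|---|---|
| 0 | 0.300 | 0.343 | 0.216 |
| 0.25 | 0.225/0.925 = 0.243 | 0.433 | 0.149 |
| 0.50 | 0.150/0.850 = 0.176 | 0.559 | 0.082 |
| 0.80 | 0.060/0.760 = 0.079 | 0.781 | 0.018 |

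The direction is the same for any s above zero; at s = 0 there is no bias.

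**Replacement.** With one or two non-evaluable patients among the first 9, Study Design enrols replacements, whereas Sections 9.1 and 9.2 enrol none and continue with 8 or 7 evaluable. Section 9.2's extra cohorts start at three losses. The phrase about the first cohort in Study Design is also unclear. Its contrast with the expansion cohort suggests the whole escalation part. If it means only the first three men, Study Design has no rule for later escalation cohorts.

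**Expansion size and total, with m non-evaluable patients in escalation.**

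- Study Design, reading replacement as covering all of escalation: (9 + m) + (9 − m) = 18. The expansion is 9, 8, 7, 6 for m = 0, 1, 2, 3. At m = 4 it would be 5, below the stated minimum of 6.
- Section 9.2, m = 0 to 2: 9 + 6 to 9 + 9 = 15 to 18.
- Section 9.2, m = 3, with the extra cohort of 3 fully evaluable: 12 + 6 to 12 + 9 = 18 to 21.

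Section 9.2 does not say which DLT results give 6, 7, 8 or 9.

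**The case against.** The strongest reply is that Study Design is an answer in an application form, which asks for at least a summary and allows protocol pages to be attached, while Section 9 is the protocol's own statistical text and already holds a sound definition. On this view the missing window and toxicity exception are omissions from a summary. That has force for evaluability, and it makes the repair easy. It does not cover replacement or expansion size, where Study Design states a different rule. Nor is Study Design marked as superseded: the form carries an IRB approval of 1/12/2023, the Section 9 pages are dated 15SEPT2020, and no clause in the supplied text settles precedence.

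Other points stand in part:

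- The Study Design bullets say evaluable, not DLT-evaluable. Equating the two is an inference, though that text offers no other definition. The definition of a DLT is not in the supplied text and might treat early DLTs separately.
- The example pairs Study Design's evaluability rule with the Section 9.1.1 table. Study Design's own copy prints the escalation sign the other way, which cannot be meant literally. The 0/3 result also needs both replacements to be DLT-free.
- The monitoring committee reviews serious adverse events and dose levels, and Section 9.1's 90-day safety criteria cover everyone who received any drug. Early toxicity would therefore be visible elsewhere, though not in the DLT rate.

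A reader might go further and infer two things that the documents do not support. One is that finishing escalation with 7 or 8 evaluable patients breaches a minimum of 9. The plan is for up to 9; the minimum belongs only to the clause triggered by three or more losses, and the decision table covers n = 7 and 8. The other is that the total of 18 is contradicted. It is a planned figure, and 12 + 6 = 18 remains possible with three losses.

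**Conclusion.** The point holds as a conflict between Study Design and Section 9 that needs correcting. Replacement and the driver of expansion size are in direct conflict. Evaluability differs through what Study Design leaves out, but applied as written its rule removes early-stopping DLT patients from the primary rate and can turn a de-escalation into an escalation.

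The direction of the bias is downward whenever any DLT patient is excluded. Its size is not known. The apparent rates of 24%, 18% and 8% for a true 30% rest on assumed exclusion shares of 25%, 50% and 80% and should not be read as estimates for this trial. They also depend on the unseen DLT definition not rescuing early DLTs. The effect reaches beyond the DLT rate, because Section 9.4 uses the same population for the secondary endpoints.

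**What to change.** 1. Use one definition of DLT-evaluable in Study Design, Section 9 and the expansion: the one already in Section 9.1, with its 30-day window and toxicity exception. Add that any patient with a DLT in that window is counted in the DLT rate, since Section 9.1 does not cover a DLT patient who falls short for another reason. This is a wording change with no added patients. It also fixes the population for Section 9.4.
2. Reconcile Study Design with Sections 9.1 and 9.2 into one replacement rule and say which cohorts it covers. The choice is the sponsor's, provided that a patient who stopped because of toxicity is not classed as non-evaluable.
3. Reconcile the two expansion-size rules into one. If the DLT-rate rule is kept, state which results give 6, 7, 8 or 9 patients. If the subtraction is kept, state what happens beyond three losses. If Section 9.2's extra cohorts are kept, note that the total can exceed the planned 18: 18 to 21 with three losses, if the extra cohort is fully evaluable.

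Items 2 and 3 need one sponsor decision. Replacement with subtraction holds the total at 18 for up to three losses but shrinks the expansion from 9 towards 6. Extra cohorts without subtraction protect the expansion but can add up to 3 patients at three losses. If escalation is already complete, record which rules were applied.

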#### 9.1.1 Dose Escalation / De-escalation Decision Rule

	Number of patients Treated									
Decision Rule	1	2	3	4	5	6	7	8	9	
Escalate (or highest) if # DLT <=	0	0	0	0	1	1	1	1	2	
De-escalate (or lowest) if # DLT >=	1	1	2	2	2	3	3	3	4	
Eliminate (or stop) if # DLT >=			3	3	4	4	5	5	5	

Note: the next cohort will be treated at the current dose level if the criteria are not met for escalation/de-escalation rules.

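### The escalation row in the IRB-approved Study Design section carries the reverse inequality sign to SAP Section 9.1.1, so at 1 to 4 patients every DLT count, including 3 of 3, meets the criterion to escalate

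*Combined protocol and SAP*

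**What the plan says.** Both texts describe a BOIN escalation with cohorts of three, a target DLT rate of 30% and up to 9 DLT-evaluable patients in the escalation part. Each gives a decision table for 1 to 9 patients treated.

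- **Application, Study Design** (IRB approval dated 1/12/2023). The three rows are "Escalate (or highest) if # DLT >= 0 0 0 0 1 1 1 1 2", then "De-escalate (or lowest) if # DLT >= 1 1 2 2 2 3 3 3 4", then "Eliminate (or stop) if # DLT >= -- -- 3 3 4 4 5 5 5". All three carry the same sign. There is no instruction for repeating a dose, and none on which row prevails when a count meets more than one.
- **SAP Section 9.1.1** (version date 15 September 2020). The numbers in all three rows are identical and the de-escalate and eliminate rows carry the same sign as in the application. The first row, however, reads "Escalate (or highest) if # DLT <=". A note adds that "the next cohort will be treated at the current dose level if the criteria are not met for escalation/de-escalation rules".

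Both are current text. The difference does not come from an amendment log.

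**The concern.** The table is the rule by which the trial meets its primary objective, finding the maximum tolerated dose, and it is the main protection against over-dosing during escalation. The two versions give opposite meanings to the same escalation numbers. The version in the application also contradicts the two rows beneath it, so someone working from it alone cannot derive a single action from a cohort result, and the row does not enforce the stated 30% target.

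The more worrying case is not the absurd one. A reader who sees that 3 DLTs in 3 patients satisfies the escalate row will suspect a misprint. A reader who sees 1 in 3 will not, because no other row competes with it.

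**Working it through.** **Inputs.** Target φ = 0.30 (both texts); cohort size 3 (both texts); thresholds from the two tables. The BOIN interval limits are not stated, so I assume the usual ones: φ₁ = 0.6φ = 0.18, φ₂ = 1.4φ = 0.42, and elimination when Pr(p > 0.30 | data) > 0.95 under a uniform prior with at least 3 patients.

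**Step 1: reproduce the printed thresholds.**

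- λₑ = log[(1 − φ₁)/(1 − φ)] / log[φ(1 − φ₁)/(φ₁(1 − φ))] = log(0.82/0.70) / log(0.246/0.126) = 0.2365
- λ_d = log[(1 − φ)/(1 − φ₂)] / log[φ₂(1 − φ)/(φ(1 − φ₂))] = log(0.70/0.58) / log(0.294/0.174) = 0.3585

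The rule is to escalate if DLTs ≤ floor(nλₑ) and to de-escalate if DLTs ≥ ceil(nλ_d).

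| n | 1 | 2 | 3 | 4 | 5 | 6 | 7 | 8 | 9 |
|---|---|---|---|---|---|---|---|---|---|
| nλₑ | 0.236 | 0.473 | 0.709 | 0.946 | 1.182 | 1.419 | 1.655 | 1.892 | 2.128 |
| floor | 0 | 0 | 0 | 0 | 1 | 1 | 1 | 1 | 2 |
| nλ_d | 0.359 | 0.717 | 1.076 | 1.434 | 1.793 | 2.151 | 2.510 | 2.868 | 3.227 |
| ceil | 1 | 1 | 2 | 2 | 2 | 3 | 3 | 3 | 4 |

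The posterior rule gives elimination at 3, 3, 4, 4, 5, 5, 5 for n = 3 to 9. All 25 printed numbers (9 + 9 + 7) match. The escalation numbers come from rounding down, so they are upper limits and are correct only with ≤.

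**Step 2: list which counts meet each row.**

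| n | Escalate, as printed (≥) | Escalate, SAP (≤) | De-escalate | Eliminate | Repeat dose, SAP |
|---|---|---|---|---|---|
| 3 | 0–3 | 0 | 2–3 | 3 | 1 |
| 4 | 0–4 | 0 | 2–4 | 3–4 | 1 |
| 5 | 1–5 | 0–1 | 2–5 | 4–5 | none |
| 6 | 1–6 | 0–1 | 3–6 | 4–6 | 2 |
| 9 | 2–9 | 0–2 | 4–9 | 5–9 | 3 |

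- At n = 1 to 4 the printed row is met by every count.
- At n = 5 to 9 it is inverted: 0 of 6 does not qualify for escalation and 6 of 6 does; 0 or 1 of 9 does not and 9 of 9 does.
- At every n from 1 to 9, each count that meets de-escalate or eliminate also meets the printed escalate row. With ≤, escalate and de-escalate overlap at no n.

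**Step 3: chance of meeting the escalate row.** With Y ~ Binomial(n, p), the SAP sign at n = 3 gives P(Y = 0) = (1 − p)³, and the printed sign gives P(Y ≥ 0) = 1.

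| True DLT rate | n = 3: printed / SAP | n = 6: printed / SAP | n = 9: printed / SAP |
|---|---|---|---|
| 10% | 1.000 / 0.729 | 0.469 / 0.886 | 0.225 / 0.947 |
| 30% | 1.000 / 0.343 | 0.882 / 0.420 | 0.804 / 0.463 |
| 50% | 1.000 / 0.125 | 0.984 / 0.109 | 0.980 / 0.090 |

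At n = 6 and n = 9, the printed row becomes more likely to be met as toxicity rises.

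**Step 4: how often the ambiguous counts arise in a cohort of three.** One DLT in three has probability 3p(1 − p)²: at p = 0.30, 3 × 0.30 × 0.49 = 0.441; at p = 0.50, 0.375. Two or three DLTs, where the printed rows conflict openly, have probability 0.216 at p = 0.30 and 0.500 at p = 0.50.

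**The case against.** The strongest answer is that the plan already holds the correct rule. Section 9.3 bases escalation decisions and the MTD on Section 9.1.1, and Section 9.1 uses the same table to choose the expansion dose. The Study Design text is a field in an application form that invites a summary and allows protocol pages to be attached. A condition that every count satisfies is empty, and the rows beneath it, the named design and the 30% target all point to a typing slip. On this view the 100% describes one row read in isolation, not how often the trial would escalate. Nothing suggests that any cohort was assigned from the misprinted row.

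Much of this stands. The SAP table is right, an informed reader would suspect a misprint, and the percentages are chances of meeting the row, not operating characteristics of the trial. But nothing in the Study Design section defers to Section 9.1.1, and the form carries the later date. The slip is also not evident everywhere in the table: 1 of 3 meets the escalate row with no competing row, and that is the count for which the SAP requires the dose to be repeated.

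Two factual doubts remain. First, inequality signs elsewhere in the form are damaged in the available text; the age and ECOG limits appear with a bare equals sign. A two-character ≥ substituted for ≤ is an unlikely result of that kind of loss, but the source page should be looked at. Second, the form's answer on whether enrolment stays open is not legible. If escalation is already complete, the table guides no future cohort, but the record still needs correcting and past decisions still need confirming.

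**Conclusion.** The point holds and must be fixed. The escalation row in the IRB-approved Study Design section is wrong as written, and the row in Section 9.1.1 is right. At the planned cohort size the printed row is met by 4 of 4 possible counts, against 1 of 4 in the SAP.

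The conflict between the two tables, and the overlap of rows within the application's table, can be read directly from the text and need no assumption. The identification of ≤ as the correct sign uses the usual BOIN settings, which neither text states; the exact match to all 25 printed numbers supports them strongly. The practical risk is reduced by the SAP's reliance on its own table. This is an error of transcription, not a flaw in the underlying design, but it affects the dose-decision rule on which the primary objective depends.

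**What to change.** 1. In the Study Design table, change the sign in the escalation row from ≥ to ≤, so that it matches Section 9.1.1. Leave all the numbers as they are.
2. Add the Section 9.1.1 note on repeating the current dose when neither criterion is met, and state that Section 9.1.1 governs if the texts differ.
3. Confirm for every n from 1 to 9 that no count meets both escalate and de-escalate; the enumeration shows that the corrected table passes.
4. Check the source page of the form, then document which table was used for each cohort decision already taken, with particular attention to any cohort with 1 DLT in 3 patients.

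The cost is a one-character correction and one added note through an IRB amendment, plus a short review of past decisions. Sample size, thresholds and analyses do not change.
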